8.1.5.3.2 Follow-up Visits

Subjects who discontinue trial treatment for a reason other than disease progression will move into the Follow-Up Phase and should continue surveillance per standard of care. This includes

physician visits with labs (CEA and CA 19-9) every 3 months until year 3 post surgery and then every 6 months until year 5 post surgery as well as CT scan of chest/abdomen/pelvis with IV/PO contrast (or MRI abdomen/pelvis plus noncontrast chest CT if iodinated dye cannot be administered) annually for 2 years and then on an as needed basis.

Every effort should be made to collect information regarding disease status until the start of new anti-neoplastic therapy, disease progression, death, or end of the study. Information regarding post-study anti-neoplastic treatment will be collected if new treatment is initiated.

8.1.5.3.3 Survival Follow-up

Participants who experience confirmed disease progression or start a new anticancer therapy, will move into the Survival Follow-Up Phase and should be contacted by telephone every 12 weeks to assess for survival status until death, withdrawal of consent, or the end of the trial, whichever occurs first.

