7.0 TRIAL FLOW CHART

7.1 Study Flow Chart

Pre-treatment research biopsy for pathologist review	X								
Pre-treatment biopsy for biomarker analysis ^c	X								
Resected surgical specimen for pathologist review						X			
Resected surgical specimen for biomarker analysis ^{c,d}						X			
Foundation One CDx	X					X ^d			
Guardant 360 ctDNA collection and blood banking ^l	X				X		X		X ^k
Stool collection	X				X		X		X ^k

^aCT scan of chest/abdomen/pelvis with IV and PO contrast, OR MRI of abdomen/pelvis plus non-contrast chest CT if contraindication to iodinated dye.

^bOnly needed in women of childbearing potential

^cBiomarker analysis includes testing for MSI via immunohistochemistry (IHC), HER2 testing (via IHC and/or fluorescence in situ hybridization (FISH)), Epstein-Barr encoding region in situ hybridization (EBER ISH), PD-L1 CPS testing, and whole-exome RNAseq expression

^dWill only be able to be performed if there is residual tumor left in surgical specimen

^eSurveillance visits with physician (or nurse practitioner or physician assistant) will occur every 3 months until year 3 post surgery, and then every 6 months until year 5 post surgery

^fSurveillance imaging will be performed annually for 2 years post-surgery and then as clinically indicated

^gWill only be performed as needed

^hWill be checked every 3 months until year 3 post surgery, and then every 6 months until year 5 post surgery

ⁱTSH only be checked, and FT4 and T3 only checked reflexively if TSH is abnormal, per routine care.

^jPatients will come off study 5 years post-surgery, if cancer recurs, or if patient withdraws consent. However, overall survival follow-up will continue to year 5 if cancer recurs or if patient withdraws consent from treatment but not follow up.

^kWill only be collected if patient's gastroesophageal cancer recurs

^lBlood Banking collected and processed per IRB16294A (see [Section 8.1.2.6](#) of this protocol).

^mEndoscopy must be conducted at enrolling institution (see [Section 8.1.2.6.2](#) of this protocol).

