8.1.1.5.3 Subsequent Anti-Cancer Therapy Status

The investigator or qualified designee will review all new anti-neoplastic therapy initiated after the last dose of trial treatment. If a participant initiates a new anti-cancer therapy within 30 days after the last dose of trial treatment, the safety follow-up visit must occur before the first dose of the new therapy. Once new anti-cancer therapy has been initiated the participant will move into survival follow-up.

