8.1.2.5.2 Tumor Imaging During the Study

The first on-study imaging assessment (CT chest/abdomen/pelvis with IV/PO contrast) should be performed at 8 weeks (56 days ± 3 days) from the date of allocation. PET/CT, EUS, and upper endoscopy will also be performed at this time. Subsequent tumor imaging (CT chest/abdomen/pelvis with IV/PO contrast) should be performed 6-10 weeks post-operatively. Thereafter, surveillance imaging will be performed as per standard of care at this institution (annually for 2 years post-surgery and then as clinically indicated). Scans will be evaluated for progression or new lesions as per RECIST 1.1. If a reason exists precluding use of iodinated contrast, MRI abd/pelvis and noncontrast chest CT can be substituted. Surveillance EGD will only be performed as clinically indicated.

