8.1.2.5.3 End of Treatment and Follow-up Tumor Imaging

In participants who discontinue study treatment without documented disease progression, every effort should be made to continue monitoring their disease status by tumor imaging using the same imaging schedule used while on treatment (6-10 weeks after surgery, then annually to year 2, and then as needed) to monitor disease status until the start of a new anticancer treatment, disease progression, pregnancy, death, withdrawal of consent, or the end of the study, whichever occurs first.

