8.1.2.5.4 RECIST 1.1 Assessment of Disease

RECIST 1.1 will be used as the primary measure for assessment of tumor response, date of disease progression/recurrence, and as a basis for all protocol guidelines related to disease status (eg, discontinuation of study treatment).

8.1.2.5.5 iRECIST Assessment of Disease

iRECIST is based on RECIST 1.1, but adapted to account for the unique tumor response seen with immunotherapeutic drugs. When clinically stable, participants should not be discontinued until progression is confirmed by the Investigator, working with local radiology, according to the rules below. This allowance to continue treatment despite initial radiologic PD takes into account the observation that some participants can have a transient tumor flare in the first few months after the start of immunotherapy, and then experience subsequent disease response.

A description of the adaptations and iRECIST process is provided in [Appendix 4](#), with additional detail in the iRECIST publication. [45] iRECIST will be used by the Investigator to assess tumor response and progression/recurrence, and make treatment decisions.

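### Starting new anticancer therapy before recurrence moves a patient to survival-only telephone follow-up, so later recurrences may go unrecorded for DFS; the bias can go either way and is probably small

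*Combined protocol and SAP*

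**What the plan says.** Two sections make new therapy sufficient by itself to end disease follow-up. Section 8.1.5.3.3 joins two triggers with an 'or': confirmed progression, or patients who "start a new anticancer therapy, will move into the Survival Follow-Up Phase and should be contacted by telephone every 12 weeks", with survival status as the only stated purpose of the call. Section 8.1.1.5.3 repeats it: "Once new anti-cancer therapy has been initiated the participant will move into survival follow-up".

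Two more sections, both about participants who discontinue study treatment without progression, stop collection at the same moment. Section 8.1.2.5.3 continues imaging "to monitor disease status until the start of a new anticancer treatment" (among other end points). Section 8.1.5.3.2 says: "Every effort should be made to collect information regarding disease status until the start of new anti-neoplastic therapy". It also says: "Information regarding post-study anti-neoplastic treatment will be collected if new treatment is initiated".

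The flow chart (section 7.1) reads differently. Footnote e runs surveillance visits to year 5 and footnote f sets annual imaging for two years, then as clinically indicated. Neither stops at new therapy. Footnote j takes patients off study at year 5, recurrence or withdrawal of consent, and adds that "overall survival follow-up will continue to year 5 if cancer recurs or if patient withdraws consent from treatment but not follow up". New therapy is not named there. Section 8.1.2.5.2 likewise has no such stop; it says "surveillance imaging will be performed as per standard of care at this institution".

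For DFS itself, section 3.2 gives the time origin (first pembrolizumab dose) and the hypothesis of improvement over historical controls. Section 9.2 names Kaplan-Meier estimation and, if events suffice, Cox models of tumor markers on DFS. It lists no DFS events and no censoring rule. Section 8.1.2.5.4 helps only in part: "RECIST 1.1 will be used as the primary measure for assessment of tumor response, date of disease progression/recurrence".

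**The concern.** A patient who starts another therapy after surgery, with no recurrence, leaves disease follow-up under sections 8.1.1.5.3 and 8.1.5.3.3. A telephone call about survival will not reliably record a later recurrence or its date. In the DFS curve that patient is then either censored at the start of therapy or enters only as a death, later than the true event.

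Censoring at new therapy is harmless only if treated patients have the same later recurrence hazard as the rest. If therapy is given because the disease looked worse, DFS reads too high; if treated patients do better, it reads too low. The comparison with historical controls and the marker Cox models would both use these data. A censoring rule can still be written before analysis, but it cannot replace recurrence data that were not collected.

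**Working it through.** **Text.** Only the footnotes of the flow chart could be compared; its visit grid is not legible in the text available.

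| Place | Stops disease follow-up at new therapy? |
|---|---|
| 8.1.1.5.3, 8.1.5.3.3 | Yes, to survival follow-up |
| 8.1.2.5.3, 8.1.5.3.2 | Yes, for participants who discontinue treatment |
| 7.1 footnotes e, f, j; 8.1.2.5.2 | No such stop stated |

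The difference is by omission: the footnotes do not say that disease follow-up continues after new therapy.

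**Size.** The plan gives no DFS rate, no share treated before recurrence and no hazard ratio, so there is no figure of its own to reproduce. The inputs below are for illustration.

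- From section 4.2.1: 5-year survival of 42%, 57% and 68%, used as stand-ins for DFS (S5) in patients not given new therapy.
- From section 9.2: 33 patients.
- Assumed: therapy starts at τ = 0.4 years after first dose in a fraction a = 1/33, 10% or 30% of event-free patients; later hazard ratio HR = 0.5, 1, 2 or 3; constant hazards; where only deaths are seen, a mean of 1 year from recurrence to death.

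Formulas, at horizon T:

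- λ = -ln(S5)/5; S0 = exp(-λτ); Sr = exp(-λ(T-τ)); St = exp(-HR·λ(T-τ))
- True DFS = S0·[(1-a)·Sr + a·St]
- Censored at new therapy = S0·Sr
- Error = S0·a·(Sr - St): positive if HR > 1, zero if HR = 1, negative if HR < 1
- Deaths only: replace St by the probability that time to recurrence plus time from recurrence to death exceeds T-τ

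Example, S5 = 57%, a = 10%, HR = 2, T = 5:

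- λ = 0.1124, S0 = 0.9560, Sr = 0.5962, St = 0.3555
- True: 0.9560 × (0.9 × 0.5962 + 0.1 × 0.3555) = 54.7%
- Censored: 0.9560 × 0.5962 = 57.0%, an error of +2.3 points
- Deaths only: St becomes 0.4557, giving 0.9560 × (0.9 × 0.5962 + 0.1 × 0.4557) = 55.7%, an error of +1.0 point

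Range of error over the grid, in percentage points:

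| Share treated | Censored, 5 y | Censored, 2 y | Deaths only, 5 y | Deaths only, 2 y |
|---|---|---|---|---|
| 1 of 33 | -0.6 to +1.1 | -0.3 to +0.9 | +0.1 to +0.3 | +0.1 to +0.7 |
| 10% | -2.1 to +3.7 | -1.1 to +3.0 | +0.3 to +1.0 | +0.3 to +2.4 |
| 30% | -6.2 to +11.0 | -3.2 to +9.0 | +1.0 to +2.9 | +0.9 to +7.1 |

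Starting therapy at 1.0 year instead, with 10% treated, gives censoring errors of -1.7 to +3.4 (5 years) and -0.6 to +2.1 (2 years). The 2-year columns matter because section 1.0 estimates 24 months of enrollment in a 36-month trial; closure then would leave about 12 to 36 months of follow-up.

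**Against sampling error.** At 57%, SE = √(0.57 × 0.43 / 33) = 8.6 points. The matching 2-year rate is 0.57^(2/5) = 79.9%, with SE 7.0 points. The largest 5-year censoring error with 10% treated is 3.67/8.6 = 0.43 SE; with 1 of 33 it is 1.11/8.6 = 0.13 SE.

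**The case against.** The strongest reply is that the situation will be rare. Section 4.2.1 describes observation after resection as standard care, and section 9.2 says these patients typically have no additional therapy. Section 6.4.2 prohibits nothing in post-treatment follow-up, but permitting therapy is not expecting it. The 30% row is therefore unlikely. This stands, and it limits the size of the problem.

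A reader might infer that a recurrence not recorded under these rules is lost for good. The documents do not support that. Surveillance is standard of care, section 11.8 requires source documents to be kept, section 11.9 requires access to original records, and flow-chart footnote k plans ctDNA and stool collection at recurrence without excluding patients already on new therapy. Some recurrences might be recovered. But the plan does not provide for looking, and care given elsewhere may not be reachable.

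A reader might also infer that DFS feeds no formal analysis. Section 9.2 plans no test against historical controls, but it does plan marker Cox models on DFS if events suffice.

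Finally, following patients irrespective of new therapy is one choice of estimand among others. With a surgery-alone comparator, censoring at new therapy can be defended as closer to the stated comparison. That stands too. It is a reason to collect the data that allow both analyses; it does not justify stopping collection.

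**Conclusion.** The point holds on the text: sections 8.1.1.5.3 and 8.1.5.3.3 state a rule that, followed as written, can leave recurrences after new therapy unrecorded, and the flow-chart footnotes do not share it. It should be corrected, but the expected effect is small. With 10% or fewer treated before recurrence, the DFS error is under half a standard error. Every input to that figure except the 33 patients and the stand-in survival rates is assumed.

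It would go too far to say that DFS will be overstated. Under censoring, the direction depends on whether treated patients have a higher or lower later hazard, which the documents do not say. Nor do the documents show an outright contradiction: the flow chart differs by omission. The missing DFS event list and censoring rule would be a matter of detail on their own; they matter here because they leave open what happens to these patients. The pCR decision rule and OS are unaffected.

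**What to change.** Reconcile sections 8.1.1.5.3, 8.1.2.5.3, 8.1.5.3.2 and 8.1.5.3.3 with flow-chart footnotes e, f and j, so that recurrence status from visits and scans done as standard of care is recorded until recurrence, death, withdrawal of consent or year 5, whether or not new therapy has started.

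In section 9.2, state the DFS events and the censoring rule. Report DFS irrespective of new therapy and also censored at new therapy. Which of the two is primary is for the sponsor to choose, given the surgery-alone comparator. Report how many patients started therapy before recurrence; section 8.1.5.3.2 already collects later treatment.

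The cost is wording in the protocol and SAP and a few extra records, with no added procedures. The drawback is that the version ignoring new therapy includes any effect of that therapy, which must be said when it is set beside historical controls.

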8.2 Assessing and Recording Adverse Events

An adverse event is defined as any untoward medical occurrence in a patient or clinical investigation participant administered a pharmaceutical product and which does not necessarily have to have a causal relationship with this treatment. An adverse event can therefore be any unfavorable and unintended sign (including an abnormal laboratory finding, for example), symptom, or disease temporally associated with the use of a medicinal product or protocol-specified procedure, whether or not considered related to the medicinal product or protocol-specified procedure. Any worsening (i.e., any clinically significant adverse change in frequency and/or intensity) of a preexisting condition that is temporally associated with the use of the Merck's product, is also an adverse event.

Changes resulting from normal growth and development that do not vary significantly in frequency or severity from expected levels are not to be considered adverse events. Examples of this may include, but are not limited to, teething, typical crying in infants and children and onset of menses or menopause occurring at a physiologically appropriate time.

Merck product includes any pharmaceutical product, biological product, device, diagnostic agent or protocol-specified procedure, whether investigational (including placebo or active comparator medication) or marketed, manufactured by, licensed by, provided by or distributed by Merck for human use.

Adverse events may occur during the course of the use of Merck product in clinical trials, or as prescribed in clinical practice, from overdose (whether accidental or intentional), from abuse and from withdrawal.

All AEs, SAEs and other reportable safety events that occur after the consent form is signed but before treatment allocation/randomization must be reported by the investigator if the participant is receiving placebo run-in or other run-in treatment, if the event caused the

participant to be excluded from the study, or is the result of a protocol-specified intervention, including but not limited to washout or discontinuation of usual therapy, diet, or a procedure.

- All AEs from the time of treatment allocation/randomization through 30 days following cessation of study treatment must be reported by the investigator.
- All AEs meeting serious criteria, from the time of treatment allocation/randomization through 90 days following cessation of study treatment, or 30 days following cessation of study treatment if the participant initiates new anticancer therapy, whichever is earlier must be reported by the investigator.
- All pregnancies and exposure during breastfeeding, from the time of treatment allocation/randomization through 120 days following cessation of study treatment, or 30 days following cessation of study treatment if the participant initiates new anticancer therapy must be reported by the investigator.
- Additionally, any SAE brought to the attention of an investigator at any time outside of the time period specified above must be reported immediately by the investigator if the event is considered to be drug-related.

Investigators are not obligated to actively seek AE or SAE or other reportable safety events in former study participants. However, if the investigator learns of any SAE, including a death, at any time after a participant has been discharged from the study, and he/she considers the event to be reasonably related to the study treatment or study participation, the investigator must promptly notify Merck.

8.2.1 Definition of an Overdose for This Protocol and Reporting of Overdose to the Principal Investigator and to Merck

For purposes of this study, an overdose of pembrolizumab will be defined as any dose of 1,000 mg or greater (≥ 5 times the indicated dose). No specific information is available on the treatment of overdose of pembrolizumab. In the event of overdose, the participant should be observed closely for signs of toxicity. Appropriate supportive treatment should be provided if clinically indicated.

If an adverse event(s) is associated with (“results from”) the overdose of a Merck product, the adverse event(s) is reported as a serious adverse event, even if no other seriousness criteria are met.

If a dose of Merck’s product meeting the protocol definition of overdose is taken without any associated clinical symptoms or abnormal laboratory results, the overdose is reported as a non-serious Event of Clinical Interest (ECI), using the terminology “accidental or intentional overdose without adverse effect.”

All reports of overdose with and without an adverse event must be reported within 24 hours to the P.I. and within 2 working days hours to Merck Global Safety. (Attn: Worldwide Product Safety; [contact])

8.2.2 Reporting of Pregnancy and Lactation to the Principal Investigator and to Merck

Although pregnancy and infant exposure during breast feeding are not considered adverse events, it is the responsibility of investigators or their designees to report any pregnancy or lactation in a participant (spontaneously reported to them) that occurs during the study.

Pregnancies and infant exposures during breastfeeding that occur after the consent form is signed but before treatment allocation/randomization must be reported by the investigator if they cause the participant to be excluded from the trial, or are the result of a protocol-specified intervention, including but not limited to washout or discontinuation of usual therapy, diet, placebo treatment or a procedure.

Pregnancies and infant exposures during breastfeeding that occur from the time of treatment allocation/randomization through 120 days following cessation of P.I.'s product, or 30 days following cessation of treatment if the participant initiates new anticancer therapy, whichever is earlier, must be reported by the investigator. All reported pregnancies must be followed to the completion/termination of the pregnancy. Pregnancy outcomes of spontaneous abortion, missed abortion, benign hydatidiform mole, blighted ovum, fetal death, intrauterine death, miscarriage and stillbirth must be reported as serious events (Important Medical Events). If the pregnancy continues to term, the outcome (health of infant) must also be reported.

Such events must be reported within 24 hours to the P.I. and within 2 working days to Merck Global Safety. (Attn: Worldwide Product Safety; FAX [[contact]]([contact]))

8.2.3 Immediate Reporting of Adverse Events to the Principal Investigator and to Merck

8.2.3.1 Serious Adverse Events

A serious adverse event is any adverse event occurring at any dose or during any use of Merck's product that:

- Results in death;
- Is life threatening;
- Results in persistent or significant disability/incapacity;
- Results in or prolongs an existing inpatient hospitalization;
- Is a congenital anomaly/birth defect;
- Is another important medical event
- **Note:** In addition to the above criteria, adverse events meeting either of the below criteria, although not serious per ICH definition, are reportable to the Merck in the same timeframe as SAEs to meet certain local requirements. Therefore, these events are considered serious by Merck for collection purposes.
 - Is a new cancer (that is not a condition of the study);
 - Is associated with an overdose.

Refer to Table 6 for additional details regarding each of the above criteria.

For the time period beginning when the consent form is signed until treatment allocation/randomization, any serious adverse event, or follow up to a serious adverse event, including death due to any cause that occurs to any participant must be reported within 24 hours to the P.I. and within 2 working days to Merck Global Safety if it causes the participant to be excluded from the trial, or is the result of a protocol-specified intervention, including but not limited to washout or discontinuation of usual therapy, diet, placebo treatment or a procedure.

For the time period beginning at treatment allocation/randomization through 90 days following cessation of treatment, or 30 days following cessation of treatment if the participant initiates new anticancer therapy, whichever is earlier, any serious adverse event, or follow up to a serious adverse event, including death due to any cause whether or not related to the Merck product, must be reported within 24 hours to the P.I. and within 2 working days to Merck Global Safety.

Additionally, any serious adverse event, considered by an investigator who is a qualified physician to be related to Merck product that is brought to the attention of the investigator at any time following consent through the end of the specified safety follow-up period specified in the paragraph above, or at any time outside of the time period specified in the previous paragraph also must be reported immediately to Merck Global Safety.

All participants with serious adverse events must be followed up for outcome.

